11. TRIAL TREATMENT

11.1. Treatment Timelines

Radiotherapy should commence as soon as possible and ideally within 4 weeks of randomisation.

11.2. Radiotherapy Planning and Treatment

Patients entered in the PARABLE trial are randomised to receive either proton beam therapy (PBT) at The Christie (Manchester) or UCLH (London), or intensity modulated arc radiotherapy (IMAT) ideally in DIBH at their local radiotherapy centre. Radiotherapy imaging, positioning, outlining, planning and treatment (including verification) should be carried out in accordance with the guidelines in the current version of the radiotherapy planning document, available on request from ICR-CTSU ([contact]).

For PBT and IMAT, the treatment prescription is:

- 40 Gy (RBE-weighted dose for PBT) in 15 fractions (2.67 Gy (RBE-weighted dose for PBT) per fraction) over 3 weeks
- Where indicated, a simultaneous integrated boost to tumour bed of 48 Gy (RBE-weighted dose for PBT) in 15 fractions (3.2 Gy (RBE-weighted dose for PBT) per fraction) over 3 weeks and/or simultaneous integrated boost to IMN of 48 Gy (RBE-weighted dose for PBT) in 15 fractions (3.2 Gy (RBE-weighted dose for PBT) per fraction) over 3 weeks

11.3. Treatment Scheduling and Gaps

Treatment can start on any day of the week. Patients should not have a break in treatment where possible. Where interruptions are due to breakdown or unavailability of the treatment machine, patients should be transferred to a matched treatment machine in the first instance.

Where this is not possible, a gap of up to 5 consecutive days is acceptable in the event of machine service or breakdown. If the treatment machine is unavailable for more than 48 hours, please contact the QA team ([contact]) and notify the PARABLE trial manager at [contact]

11.4. Concomitant Therapy

Due to increased risk of pneumonitis with TDM-1, it is recommended that patients treated in PARABLE should not receive concomitant TDM-1 alongside IMAT or PBT. Concomitant capecitabine is also not permitted. Concomitant endocrine therapy, trastuzumab and pertuzumab *are* permitted. Please contact the ICR-CTSU if any clarification around new drugs required.

Otherwise, all medication considered necessary for the patients' welfare and which is not expected to interfere with the evaluation of the treatment may be given at the discretion of the investigator. All concomitant medications must be recorded in the patient's notes.

11.5. Non-permissible Medications/Therapies

As above, concomitant Trastuzumab emtansine (TDM-1) and/or capecitabine are not permitted alongside IMAT or PBT.

12. Radiotherapy Quality Assurance (QA)

The radiotherapy quality assurance (RT QA) programme for the PARABLE trial has been designed and will be implemented by the National Radiotherapy Trials QA (RTTQA) Group. The components of the PARABLE QA programme are described in the PARABLE Radiotherapy Planning and Delivery guidelines ("Quality Assurance (QA) pack").

The full details of the programme are available on the RTTQA group website (www.rttrialsqa.org.uk).

13. Safety Reporting

13.1. Definitions

Adverse Event (AE)

An AE is any untoward medical occurrence in a patient administered a study treatment; the event does not necessarily have a causal relationship with the treatment.

Serious Adverse Event (SAE)

An SAE is any untoward medical occurrence that occurs after the first study intervention and within 30 days of the last treatment administration and:

- results in death,
- is life-threatening
- requires hospitalisation or prolongation of existing inpatients' hospitalisation
- results in persistent or significant disability or incapacity
- is a congenital anomaly or birth defect

Important adverse events that are not immediately life-threatening or do not result in death or hospitalisation but may jeopardise the subject or may require intervention to prevent one of the other outcomes listed in the definition above, may also be considered serious.

Progression of the indicated disease, death due to progression of the indicated disease and planned hospital admissions (e.g. for surgery) are not considered SAEs and do not need to be reported as such but should be reported on the appropriate eCRF as required.

Pregnancy or aid in the conception of a child whilst participating in a trial is not itself considered an SAE but should be followed up for congenital anomalies or birth defects.

Serious Adverse Reaction (SAR)

A serious adverse reaction is an SAE that is suspected as having a causal relationship to the trial treatment, as assessed by the investigator responsible for the care of the patient. A suspected causal relationship is defined as possibly, probably or definitely related (see definitions of causality table).

Definitions of causality

| Relationship | Description |
|----------------|--|
| Unrelated | There is no evidence of any causal relationship with the trial treatment |
| Unlikely | There is little evidence to suggest there is a causal relationship (e.g. the event |
| | did not occur within a reasonable time after administration of the trial |
| | treatment). There is another reasonable explanation for the event (e.g. the |
| | patient's clinical condition, other concomitant treatment) |
| Possible | There is some evidence to suggest a causal relationship (e.g. because the event |
| | occurs within a reasonable time after administration of the trial treatment). |
| | However, the influence of other factors may have contributed to the event (e.g. |
| | the patient's clinical condition, other concomitant treatments) |
| Probable | There is evidence to suggest a causal relationship, and the influence of other |
| | factors is unlikely |
| Definitely | There is clear evidence to suggest a causal relationship, and other possible |
| | contributing factors can be ruled out |
| Not assessable | There is insufficient or incomplete evidence to make a clinical judgement of the |
| | causal relationship. |

Related Unexpected Serious Adverse Event

An adverse event that meets the definition of serious and is assessed by the CI or nominative representative as:

- "Related" that is, it resulted from administration of any of the research procedures, and
- "Unexpected" that is, the type of event that is not considered to be an expected occurrence by the Chief Investigator

13.2. Reporting Adverse Events to ICR-CTSU

Any toxicity, sign or symptom that occurs after commencement of radiotherapy treatment and within 12 weeks of the last administration of radiotherapy treatment, which is not unequivocally due to progression of disease, should be considered an AE.

All AEs must be reported on the relevant eCRF and submitted to ICR-CTSU.

The severity of AEs should be graded according to the NCIC-CTC criteria version 5. For each AE, the highest grade observed since the last visit should be reported.

Whenever one or more toxicity/sign/symptom corresponds to a disease or a well-defined syndrome only the main disease/syndrome should be reported.

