1.1.4. Risks and benefits of proton beam therapy for this patient group

A possible solution to the problem for this patient group emerges with the technical developments afforded by PBT. The physical properties of PBT allow a sharp fall-off in radiation dose between the chest wall/breast/lymph nodal regions (where we want dose) and heart, lungs, contralateral breast (where we do not want dose). Several PBT in silico "planning studies" have demonstrated that the planned PBT mean heart dose is considerably lower than with photon RT (17, 23-25). Proof of concept has been shown in small, nonrandomised series, mainly from US, suggesting that a 5-week course of PBT to breast/chest wall and regional lymph nodes is safe, can reduce heart dose and has comparable short to medium toxicity compared with 5-week RT with low rates of local and distant relapse (23, 24, 26-35). As PBT enables full dose to the breast and nodes whilst aiming to reduce mean heart dose, it can be concluded that cancer outcomes with breast PBT will be maintained or even improved due to better dose coverage of breast and nodes. Given the extremely low event rates for local breast cancer relapse, it would be infeasible to test this endpoint within a randomised comparison of PBT versus photon RT.

There is a higher risk of a second primary breast cancer in young women (< 40 years) following RT if mean dose to a quadrant of the contralateral breast exceeds 1Gy (36). In the patient group eligible for PARABLE this is often exceeded as coverage to target and minimisation of heart dose may be prioritised. Use of PBT could decrease the risk of an upper inner quadrant contralateral breast cancer six fold (37). PBT may also reduce dose to lungs and oesophagus reducing the risk of late radiation-induced lung and oesophageal cancers (25). However, unlike risk of major cardiac events and heart dose, there are as yet no validated models to estimate these risks.

Despite these potential advantages of PBT there has nevertheless been some evidence from non-randomised studies of increased adverse effects in patients receiving PBT for breast cancer, including skin reactions (28, 29) and rib fractures (38, 39). PARABLE will enable randomised comparisons of early and late toxicities to assess non-inferiority and superiority of PBT versus photon RT.

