10.2. On-treatment Assessments

The following assessments should be conducted in weeks 1-3 on treatment

- Early skin and oesophageal toxicity (CTCAE v5.0) and adverse events (clinician reported)
- PRO of early toxicity and QoL including skin, breast pain and swelling, fatigue, insomnia, mouth /throat sores, cough and breathlessness, emotional functioning, cognitive functioning, sexual functioning, social functioning, EQ-5D-5L

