10.3. Post-Treatment Assessments

The following assessments should be conducted 2 weeks' post-treatment (5 weeks from date treatment commenced) and then weekly until acute local symptoms ≤1

Early skin and oesophageal toxicity (CTCAE v5.0) and adverse events (clinician reported).
 Assessments can be conducted remotely (i.e. via telephone) where patient attendance at clinic is not required.

The following assessments should be conducted weekly (from week 4) until week 12

 PRO of early toxicity and QoL including skin, breast pain and swelling, fatigue, insomnia, mouth /throat sores, cough and breathlessness, emotional functioning, cognitive functioning, sexual functioning, and social functioning, with the addition of EQ-5D-5L and healthcare resource use at the 12 week time point

On-treatment PRO/QoL booklets will be provided at participating centres for patients to complete in clinic. Post-treatment, patients will receive a questionnaire booklet to take home to complete from week 4 (from date treatment commenced) onwards (to 12 weeks). From the 6-month post-treatment follow-up assessment booklets will be sent to participants' homes directly by ICR-CTSU.

Where assessments are conducted remotely, any medical and/or psychological concerns identified should be followed by appropriate local clinical review. Patients completing questionnaire booklets are instructed to contact the local clinical team should they experience any distress or concerns resulting from the questions asked.

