10.8. Discontinuation from Follow-up

If a patient no longer wishes to attend follow-up visits:

If a patient chooses to withdraw from further follow-up, centre personnel should confirm whether the patient simply no longer wishes to attend trial follow up visits but is happy for the information to be collected from other sources, or whether the patient has withdrawn consent for any further information to be sent to the ICR-CTSU. ICR-CTSU should be informed via completion of the relevant forms in the eCRF.

If a patient no longer wants their data to be sent to ICR-CTSU:

In the very rare event that a patient requests that the ICR-CTSU can no longer collect information on them from routine data sources, the implications of this should be discussed with the patient first to ensure that this is their intent and, if confirmed, ICR-CTSU should be notified in writing.

Schedule of Assessments

| | | On- treatment | | | Post - treatment Time from s | | | Follow up | | | | | | | |
|---|--|------------------|--------|--------|------------------------------------|--------|--------|-----------|----------|-----------|---------|---------|---------|---------|---------------------|
| Visit/Assessment | Baseline Assessments (Pre- randomisation) | Week 1 | Week 2 | Week 3 | Week 4 | Week 5 | Week 6 | Week 12 | 6 months | 12 months | 2 years | 3 years | 4 years | 5 years | Long term follow-up |
| Informed consent | х | | | | | | | | | | | | | | |
| Randomisation checklist | х | | | | | | | | | | | | | | |
| Baseline PRO/QoL measures, health resource usage | х | | | | | | | | | | | | | | |
| Medical history | х | | | | | | | | | | | | | | |
| Weight and height measurement | х | | | | | | | | | | | | | | |
| Baseline signs & symptoms (CTCAE v5.0, RTOG) | х | | | | | | | | | | | | | | |
| Early skin & oesophageal toxicity (CTCAE v5.0) and adverse events | | Х | Х | Х | | Х | Xa | | | | | | | | |
| PRO - Early toxicity | | Х | Х | Х | Х | Х | Хp | Х | | | | | | | |
| Cough & breathlessness assessment (RTOG) | | | | | | | | Х | Х | Xc | | | | | |
| PRO – Late toxicity | | | | | | | | | Х | Х | Х | | | х | |
| Non-contrast chest CT scan | | | | | | | | | | | Х | | | | |
| Biochemistry profile | | | | | | | | | | | Х | | | | |
| Clinician-reported late toxicity | | | | | | | | | | х | х | х | х | Х | |
| Assessment for recurrence and survival | | | | | | | | | | Х | Х | Х | Х | Х | Х |
| Recording adjuvant treatment administered | | | | | | | | | | | | | | Х | |

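### Adverse events count until 12 weeks after the last fraction, but scheduled clinician collection can stop at 2 weeks, at a time set by local reaction

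*Protocol*

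**What the plan says.** **Window.** Section 13.2 counts as an adverse event any toxicity, sign or symptom that starts after radiotherapy begins and "within 12 weeks of the last administration of radiotherapy treatment, which is not unequivocally due to progression of disease, should be considered an AE". It adds that "All AEs must be reported on the relevant eCRF and submitted to ICR-CTSU", and sets the grading rule: "For each AE, the highest grade observed since the last visit should be reported".

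**Collection.** On treatment, section 10.2 lists clinician-reported adverse events in the same item as early skin and oesophageal toxicity, in weeks 1-3. Section 10.3 repeats that combined item at two weeks after treatment, which it equates to week 5 from start, "and then weekly until acute local symptoms ≤1". The Schedule of Assessments has one row for both, "Early skin & oesophageal toxicity (CTCAE v5.0) and adverse events". It is marked at weeks 1, 2, 3 and 5 and, under footnote a with the same stopping condition, at week 6. It is blank at week 12 and at every later column.

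**Other assessments inside the window.** Section 10.3 has weekly patient-reported early-toxicity booklets from week 4 to week 12. Section 10.4 has a clinician RTOG score for cough and breathlessness at 3 months, timed from the start of treatment. Neither is described as adverse event collection.

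**Possible difference between arms.** Section 1.1.4 acknowledges some non-randomised evidence of "increased adverse effects in patients receiving PBT for breast cancer, including skin reactions".

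**The concern.** The protocol has one rule for what counts as an adverse event and another for when anyone is scheduled to ask about it, and they do not match. The grading rule in 13.2 depends on visits, yet for many patients no further visit collecting adverse events may be scheduled for most of the window.

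The end of scheduled enquiry is also not a fixed date. It depends on how quickly the acute local reaction settles, which is itself an outcome of treatment. Patients with slower-settling reactions are asked about all adverse events, including those unrelated to the breast or oesophagus, for longer. If the time to settle differs between proton and photon treatment, so does the time over which non-local events are elicited. A table of adverse events by arm could then show a difference, or hide one, because of how long patients were asked. Section 14.5 has the data monitoring committee review accumulating data at least annually, and it would see the same tables.

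**Working it through.** The plan gives no figure to reproduce here; the check is timeline arithmetic.

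**Inputs**
- Treatment lasts 3 weeks: 40 Gy "in 15 fractions (2.67 Gy (RBE-weighted dose for PBT) per fraction) over 3 weeks" (section 11.2).
- The adverse event window closes 12 weeks after the last fraction (13.2).
- The earliest last scheduled adverse event collection is 2 weeks after the last fraction (10.3).
- Patient-reported early toxicity runs to week 12 from start (10.3).
- RTOG cough and breathlessness is recorded at 3 months from start (10.4), placed under week 12 in the Schedule.
- The SAE window closes 30 days after the last fraction (13.3).

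**Step 1: the window on the clock from start.** 3 + 12 = week 15.

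**Step 2: earliest end of scheduled clinician collection.** 3 + 2 = week 5, which agrees with the equivalence given in 10.3.

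**Step 3: the uncovered tail.** If the local reaction settles to grade 1 or below k weeks after the last fraction (k from 2 to 12), the part of the window without scheduled clinician adverse event collection is 12 − k weeks.

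| Reaction at grade 1 or below by | Weeks uncovered | Share of the 12 post-treatment weeks |
|---|---|---|
| k = 2 (week 5) | 10 | 10/12 = 83% |
| k = 4 (week 7) | 8 | 8/12 = 67% |
| k = 6 (week 9) | 6 | 6/12 = 50% |
| k = 12 (week 15) | 0 | 0% |

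As a share of the whole window from the start of treatment, the k = 2 case is 10/15 = 67%.

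**Step 4: what remains in the tail.** Counting the patient booklets and the 3-month RTOG score as assessments of some kind, the stretch with nothing scheduled is about weeks 12 to 15: 15 − 12 = 3 weeks, or 3/12 = 25% of the post-treatment window. The booklets cover listed symptoms and the RTOG score covers two, so neither would record an event off those lists.

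**Step 5: the SAE window.** In the k = 2 case the last scheduled adverse event contact is at about day 14 after the last fraction, 30 − 14 = 16 days before the SAE window closes.

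**Step 6: dependence on arm.** The tail is 12 − k, so a difference between arms in the distribution of k is a difference in duration of enquiry. The condition is acute local symptoms, in an item covering skin and oesophagus. Section 1.1.4 reports some evidence of more skin reactions with protons, which would lengthen enquiry in that arm. It also says protons may reduce oesophageal dose, which could shorten it. The documents fix neither the direction nor the size.

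**The case against.** The strongest reply is that a reporting window is not a visit schedule. Section 13.2 obliges sites to report all adverse events to 12 weeks whether or not a visit is due, and the 3-month clinician contact falls inside the window. Weekly patient booklets run to week 12 in both arms whatever the skin grade, and they cover non-local symptoms such as fatigue, insomnia, cough, breathlessness and throat soreness. Patients are told to contact their local team with concerns. SAEs have their own 30-day window and 24-hour reporting.

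Much of this stands. It would be wrong to say that most of the window is unassessed, that collection stops at two weeks for everyone, or that skin reaction alone sets the length. What the reply does not supply is scheduled, open enquiry about adverse events in every patient. A fixed symptom list cannot pick up an unlisted event, and a general duty without an enquiry relies on spontaneous report. Section 1.1.6 itself notes under-reporting of side effects when clinician reports are the only source.

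A reader might go further and infer that treatment comparisons will be falsely significant. The documents do not support that. Section 14.3.2.2 defines clinician-recorded early toxicity as skin and oesophageal grades, section 14.4 compares toxicities at specific time points, and no test of all-cause adverse event frequency is planned. Any false-positive rate would rest on assumed event rates, an assumed whole-arm shift in stopping time and no reporting after collection stops. The stop is per patient and none of these inputs is in the protocol, so no such figure is offered here.

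**Conclusion.** The mismatch is real and lies in the current text. Section 13.2 requires adverse events to about week 15, while sections 10.2 and 10.3 and the Schedule can end scheduled clinician collection at week 5. Up to 10 of the 12 post-treatment weeks are then without it, and fewer in patients whose reaction takes longer to settle. This assumes a 3-week course without gaps and follow-up timed from the start of treatment, as section 10.4 states.

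The consequence is limited to adverse event summaries by arm, in reports and before the data monitoring committee, which could reflect unequal ascertainment. Whether they would, and in which direction, depends on arm differences in time to settle that the documents do not give. Mean heart dose, 2-year breast symptoms and the planned skin and oesophageal comparisons are untouched. The point merits correction because the remedy is cheap and makes safety ascertainment equal in both arms.

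**What to change.** Reconcile sections 10.3 and 10.4 and the Schedule of Assessments with section 13.2:

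- Add adverse event collection for every patient at the existing 3-month clinician contact, whatever the local symptom grade, recording highest grade since the last visit and date of onset.
- Use the existing 6-month contact to capture onsets between the 3-month contact and 12 weeks after the last fraction (about weeks 12 to 15 from start).
- Summarise adverse events by arm over that fixed window, using onset dates.
- Keep the conditional weekly assessments after week 5 for resolving skin and oesophageal reactions, and give adverse events their own Schedule row.

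The cost is an additional form at two contacts that already take place and a change to the Schedule; no new visit or procedure is needed, and section 10.3 already accepts remote assessment. The downside is slightly more data entry and longer recall: from week 5 to week 12 is about 7 weeks at the 3-month contact, and the last weeks of the window are recalled from 6 months. Recall would, however, be over the same calendar points in both arms.

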13.3. Reporting of Serious Adverse Events to ICR-CTSU

Any SAE that occurs after the commencement of radiotherapy treatment and up to 30 days following the last administration of radiotherapy treatment must be reported.

All SAEs should be reported to ICR-CTSU within 24 hours of the Principal Investigator (or designated representative) becoming aware of the event, by completing the PARABLE SAE form and emailing to:

The ICR-CTSU safety desk
[contact]
For the attention of the PARABLE Trial team

As much information as possible, including the Principal Investigator's assessment of causality, must be reported to ICR-CTSU in the first instance. Additional follow up information should be reported as soon as it is available.

All SAE forms must be completed, signed and dated by the Principal Investigator or designated representative.

13.4. Review of Serious Adverse Events

The Chief Investigator (or designated representative) will assess all reported SAEs for causality and expectedness (NB. The Chief Investigator cannot down-grade the Principal Investigator's assessment of causality.)

SAEs assessed as having a causal relationship to study treatment and as being unexpected will undergo expedited reporting to the relevant authorities and all other interested parties by ICR-CTSU (see 11.5).

Sites should respond as soon as possible to requests from the Chief Investigator or designated representative (via ICR-CTSU) for further information that may be required for final assessment of an SAE.

